8.2 Assessing and Recording Adverse Events

An Adverse Event (AE) is defined as any new untoward medical occurrence or worsening of a preexisting medical condition in a clinical investigation participant administered study drug and that does not necessarily have a causal relationship with this treatment. An AE can therefore be any unfavorable and unintended sign (such as an abnormal laboratory finding), symptom, or disease temporally associated with the use of investigational product, whether or not considered related to the investigational product.

A ***non-serious adverse event*** is an AE not classified as serious.

8.2.1 Serious Adverse Events

A ***Serious Adverse Event (SAE)*** is any untoward medical occurrence that at any dose:

- results in death
- is life-threatening (defined as an event in which the participant was at risk of death at the time of the event; it does not refer to an event which hypothetically might have caused death if it were more severe)

- requires inpatient hospitalization or causes prolongation of existing hospitalization (see **NOTE** below)
- results in persistent or significant disability/incapacity
- is a congenital anomaly/birth defect
- is an important medical event (defined as a medical event(s) that may not be immediately life-threatening or result in death or hospitalization but, based upon appropriate medical and scientific judgment, may jeopardize the subject or may require intervention [eg, medical, surgical] to prevent one of the other serious outcomes listed in the definition above.) Examples of such events include, but are not limited to, intensive treatment in an emergency room or at home for allergic bronchospasm; blood dyscrasias or convulsions that do not result in hospitalization.)
- Suspected transmission of an infectious agent (eg, pathogenic or nonpathogenic) via the study drug is an SAE.
- Unusual Failure in Efficacy (for Phase IV Canadian studies)

Although pregnancy and potential drug-induced liver injury (DILI), are not always serious by regulatory definition, however, these events must be reported within the SAEs timeline.

Any component of a study endpoint that is considered related to study therapy should be reported as an SAE (eg, death is an endpoint, if death occurred due to anaphylaxis, anaphylaxis must be reported).

The following hospitalizations are not considered SAEs:

- a visit to the emergency room or other hospital department < 24 hours, that does not result in admission (unless considered an important medical or life-threatening event)
- elective surgery, planned prior to signing consent
- admissions as per protocol for a planned medical/surgical procedure
- routine health assessment requiring admission for baseline/trending of health status (eg, routine colonoscopy)
- Medical/surgical admission other than to remedy ill health and planned prior to entry into the study. Appropriate documentation is required in these cases.
- Admission encountered for another life circumstance that carries no bearing on health status and requires no medical/surgical intervention (eg, lack of housing, economic inadequacy, caregiver respite, family circumstances, administrative reason).
- Admission for administration of anticancer therapy in the absence of any other SAEs (applies to oncology protocols)

8.2.1.1 Reporting of Serious Adverse Events Associated with Nivolumab

- All Serious Adverse Events (SAEs) that occur following the subject's written consent to participate in the study through 100 days for nivolumab or discontinuation of dosing must be reported to BMS Worldwide Safety, whether related or not related to study drug. If applicable, SAEs must be collected that relate to any later protocol-specified procedure (eg, a follow-up skin biopsy).
- Following the subject's written consent to participate in the study, all SAEs, whether related or not related to study drug, are collected, including those thought to be associated with protocol-specified procedures. The investigator should report any SAE occurring after these aforementioned time periods, which is believed to be related to study drug or protocol-specified procedure to BMS.
- An SAE report should be completed for any event where doubt exists regarding its seriousness;
- If the investigator believes that an SAE is not related to study drug, but is potentially related to the conditions of the study (such as withdrawal of previous therapy or a complication of a study procedure), the relationship should be specified in the narrative section of the SAE Report Form.

An appropriate SAE form (e.g. ex-US = CIOMS form or USA = Medwatch form) should be used to report SAEs to BMS. If you prefer to use your own Institutional form, it must be reviewed by the BMS Protocol Manager prior to study initiation to ensure that at a minimum all of the data elements on the CIOMS form are present. Note: Please include the BMS Protocol number on the SAE form or on the cover sheet with the SAE form transmission.

- - ✓ The CIOMS form is available at: <http://www.cioms.ch/index.php/cioms-form-i>
 - ✓ The MedWatch form is available at: [MedWatch 3500 Form](#)
- The Sponsor-investigator will reconcile the clinical database AE cases (**case level only**) transmitted to BMS Global Pharmacovigilance ([contact]).
 - The Investigator will request from BMS GPV&E, [contact] the SAE reconciliation report and include the BMS protocol number every 3 months and prior to data base lock or final data summary
 - GPV&E will send the investigator the report to verify and confirm all SAEs have been transmitted to BMS GPV&E.
 - The data elements listed on the GPV&E reconciliation report will be used for case identification purposes. If the Investigator determines a case was not transmitted to BMS GPV&E, the case should be sent immediately to BMS ([contact]).
- In addition to the Sponsor Investigator's responsibility to report events to the FDA, suspected serious adverse reactions (whether expected or unexpected) shall be reported by

BMS to the relevant competent health authorities in all concerned countries according to local regulations (either as expedited and/or in aggregate reports).

- In accordance with local regulations, BMS will notify sponsor investigators of all reported SAEs that are suspected (related to the investigational product) and unexpected (ie, not previously described in the IB). An event meeting these criteria is termed a Suspected, Unexpected Serious Adverse Reaction (SUSAR). Sponsor investigator notification of these events will be in the form of either a SUSAR Report or a Semi-Annual SUSAR Report.
 - ✓ Other important findings which may be reported by BMS as an Expedited Safety Report (ESR) include: increased frequency of a clinically significant expected SAE, an SAE considered associated with study procedures that could modify the conduct of the study, lack of efficacy that poses significant hazard to study subjects, clinically significant safety finding from a nonclinical (eg, animal) study, important safety recommendations from a study data monitoring committee, or sponsor or BMS decision to end or temporarily halt a clinical study for safety reasons.
 - ✓ Upon receiving an ESR from BMS, the investigator must review and retain the ESR with the IB. Where required by local regulations or when there is a central IRB/IEC for the study, the sponsor will submit the ESR to the appropriate IRB/IEC. The investigator and IRB/IEC will determine if the informed consent requires revision. The investigator should also comply with the IRB/IEC procedures for reporting any other safety information.

SAEs, whether related or not related to study drug, and pregnancies must be reported to BMS within 24 hours \ 1 Business Day of becoming aware of the event. SAEs must be recorded on either CIOMS, MedWatch, or approved site SAE form.

Pregnancies must be reported and submitted to BMS. BMS will perform due diligence follow-up using the BMS Pregnancy Form which the investigator must complete.

SAE Email Address: [contact]

SAE [contact]

If only limited information is initially available, follow-up reports are required. (Note: Follow-up SAE reports should include the same investigator term(s) initially reported.)

If an ongoing SAE changes in its intensity or relationship to study drug or if new information becomes available, a follow-up SAE report should be sent within 24 hours \ 1 Business Day to BMS using the same procedure used for transmitting the initial SAE report.

All SAEs should be followed to resolution or stabilization.

The causal relationship to study drug is determined by a physician and should be used to assess all adverse events (AE). The causal relationship can be one of the following:

Related: There is a reasonable causal relationship between study drug administration and the AE.

Not related: There is not a reasonable causal relationship between study drug administration and the AE.

The term "reasonable causal relationship" means there is evidence to suggest a causal relationship.

Adverse events can be spontaneously reported or elicited during open-ended questioning, examination, or evaluation of a subject. (In order to prevent reporting bias, subjects should not be questioned regarding the specific occurrence of one or more AEs.)

8.2.2 Nonserious Adverse Event

- Non-serious Adverse Events (AE) are to be provided to BMS in aggregate via interim or final study reports as specified in the agreement or, if a regulatory requirement [eg, IND US trial] as part of an annual reporting requirement.
- Non-serious AE information should also be collected from the start of a placebo lead-in period or other observational period intended to establish a baseline status for the subjects.

8.2.2.1 Non-serious Adverse Event Collection and Reporting

The collection of non-serious AE information should begin at initiation of study drug. All non-serious adverse events (not only those deemed to be treatment-related) should be collected continuously during the treatment period and for a minimum of 100 days for nivolumab following the last dose of study treatment.

Non-serious AEs should be followed to resolution or stabilization, or reported as SAEs if they become serious. Follow-up is also required for non-serious AEs that cause interruption or discontinuation of study drug and for those present at the end of study treatment as appropriate.

8.2.3 Laboratory Test Abnormalities

All laboratory test results captured as part of the study should be recorded following institutional procedures. Test results that constitute SAEs should be documented and reported to BMS as such.

The following laboratory abnormalities should be documented and reported appropriately:

- any laboratory test result that is clinically significant or meets the definition of an SAE
- any laboratory abnormality that required the participant to have study drug discontinued or interrupted
- any laboratory abnormality that required the subject to receive specific corrective therapy.

It is expected that wherever possible, the clinical rather than laboratory term would be used by the reporting investigator (eg, anemia versus low hemoglobin value).

8.2.4 Reporting of Pregnancy and Lactation to the BMS

If, following initiation of the investigational product, it is subsequently discovered that a study participant is pregnant or may have been pregnant at the time of investigational product exposure, including during at least 5 half-lives after product administration, the investigational product will be permanently discontinued in an appropriate manner (eg, dose tapering if necessary for participant).

The investigator must immediately notify [contact] of this event and complete one of the following forms within 24 hours of awareness of the event via either the CIOMS, MedWatch or appropriate Pregnancy Surveillance Form in accordance with SAE reporting procedures.

Protocol-required procedures for study discontinuation and follow-up must be performed on the participant.

Follow-up information regarding the course of the pregnancy, including perinatal and neonatal outcome and, where applicable, offspring information must be reported on the CIOMS, MedWatch, BMS Pregnancy Surveillance Form, or approved site SAE form. A BMS Pregnancy Surveillance Form may be provided upon request.

Any pregnancy that occurs in a female partner of a male study participant should be reported to BMS. Information on this pregnancy will be collected on the Pregnancy Surveillance Form. In order for Sponsor or designee to collect any pregnancy surveillance information from the female partner, the female partner must sign an informed consent form for disclosure of this information.

8.2.5 Other Safety Considerations

Any significant worsening noted during interim or final physical examinations, electrocardiograms, X-rays, and any other potential safety assessments, whether or not these procedures are required by the protocol, should also be recorded as a non-serious or serious AE, as appropriate, and reported accordingly.

8.3 Expedited Adverse Event Reporting

8.3.1 Expedited AE reporting for this study must **be reported to the FDA/IRB per FDA and IRB guidelines**. These requirements are briefly outlined in the tables below (Section 8.3.2). Written IND safety reports will be submitted to the FDA by the IND sponsor, for serious, unexpected suspected adverse reactions within 15 calendar days of learning of its occurrence. If the event is fatal or is deemed to be life threatening, the report will be made within 7 calendar days. The IND sponsor will also make an assessment of whether the event constitutes an unanticipated problem posing risks to subjects or others (UP). This assessment will be provided to the Emory University IRB, which, in turn will make a final determination. If the Emory IRB determines an event is a UP it will notify the appropriate regulatory agencies and institutional officials.

8.3.2 Table 6 Evaluating Adverse Events

An investigator who is a qualified physician, will evaluate all adverse events as to:

| | | |
|---|--|---|
| V4.0 CTCAE Grading | Grade 1 | Mild; asymptomatic or mild symptoms; clinical or diagnostic observations only; intervention not indicated. |
| | Grade 2 | Moderate; minimal, local or noninvasive intervention indicated; limiting age-appropriate instrumental ADL. |
| | Grade 3 | Severe or medically significant but not immediately life-threatening; hospitalization or prolongation of hospitalization indicated; disabling; limiting self-care ADL. |
| | Grade 4 | Life threatening consequences; urgent intervention indicated. |
| | Grade 5 | Death related to AE |
| Seriousness | A serious adverse event is any adverse event occurring at any dose or during any use of investigational product that: | |
| | † Results in death; or | |
| | † Is life threatening; or places the subject, in the view of the investigator, at immediate risk of death from the event as it occurred (Note: This does not include an adverse event that, had it occurred in a more severe form, might have caused death.); or | |
| | † Results in a persistent or significant disability/incapacity (substantial disruption of one's ability to conduct normal life functions); or | |
| | † Results in or prolongs an existing inpatient hospitalization (hospitalization is defined as an inpatient admission, regardless of length of stay, even if the hospitalization is a precautionary measure for continued observation. (Note: Hospitalization for an elective procedure to treat a pre-existing condition that has not worsened is not a serious adverse event. A pre-existing condition is a clinical condition that is diagnosed prior to the use of investigational products and is documented in the patient's medical history.); or | |
| | † Is a congenital anomaly/birth defect (in offspring of subject taking the product regardless of time to diagnosis); or | |
| | Is a new cancer (that is not a condition of the study) (although not serious per ICH definition, is reportable to the Sponsor within 24 hours and to BMS within 2 working days to meet certain local requirements); or | |
| | Is an overdose (whether accidental or intentional). Any adverse event associated with an overdose is considered a serious adverse event for collection purposes. An overdose that is not associated with an adverse event is considered a non-serious event of clinical interest and must be reported within 24 hours to the Sponsor and to BMS within 2 working days. | |
| | Other important medical events that may not result in death, not be life threatening, or not require hospitalization may be considered a serious adverse event when, based upon appropriate medical judgment, the event may jeopardize the subject and may require medical or surgical intervention to prevent one of the outcomes listed previously (designated above by a †). | |
| Duration | Record the start and stop dates of the adverse event. If less than 1 day, indicate the appropriate length of time and units | |
| Action taken | Did the adverse event cause investigational products to be discontinued? | |
| Relationship to investigational Product(s) | Did investigational product(s) cause the adverse event? The determination of the likelihood that investigational product(s) caused the adverse event will be provided by an investigator who is a qualified physician. The investigator's signed/dated initials on the source document or worksheet that supports the causality noted on the AE form, ensures that a medically qualified assessment of causality was done. This initialed document must be retained for the required regulatory time frame. The criteria below are intended as reference guidelines to assist the investigator in assessing the likelihood of a relationship between the test drug and the adverse event based upon the available information. The following components are to be used to assess the relationship between investigational product and the AE; the greater the correlation with the components and their respective elements (in number and/or intensity), the more likely BMS product caused the adverse event (AE): | |
| Exposure | Is there evidence that the subject was actually exposed to investigational product(s) such as: reliable history, acceptable compliance assessment (pill count, diary, etc.), expected pharmacologic effect, or measurement of drug/metabolite in bodily specimen? | |
| Time Course | Did the AE follow in a reasonable temporal sequence from administration of investigational product(s)? Is the time of onset of the AE compatible with a drug-induced effect (applies to trials with investigational medicinal product)? | |
| Likely Cause | Is the AE not reasonably explained by another etiology such as underlying disease, other drug(s)/vaccine(s), or other host or environmental factors | |

| Relationship to investigational (continued) | | The following components are to be used to assess the relationship between the test drug and the AE: (continued) |
|---|---|--|
| | Dechallenge | 
Was investigational product(s) discontinued or dose/exposure/frequency reduced? If yes, did the AE resolve or improve? If yes, this is a positive dechallenge. If no, this is a negative dechallenge. (Note: This criterion is not applicable if: (1) the AE resulted in death or permanent disability; (2) the AE resolved/improved despite continuation of the BMS product; or (3) the trial is a single-dose drug trial); or (4) BMS product(s) is/are only used one time.)
 |
| | Rechallenge | 
Was the subject re-exposed to investigational product(s) in this study? If yes, did the AE recur or worsen? If yes, this is a positive rechallenge. If no, this is a negative rechallenge. (Note: This criterion is not applicable if: (1) the initial AE resulted in death or permanent disability, or (2) the trial is a single-dose drug trial); or (3) BMS's product(s) is/are used only one time).
 
NOTE: IF A RECHALLENGE IS PLANNED FOR AN ADVERSE EVENT WHICH WAS SERIOUS AND WHICH MAY HAVE BEEN CAUSED BY investigational PRODUCT, OR IF REEXPOSURE TO BMS PRODUCT POSES ADDITIONAL POTENTIAL SIGNIFICANT RISK TO THE SUBJECT, THEN THE RECHALLENGE MUST BE APPROVED IN ADVANCE BY THE SPONSOR AS PER DOSE MODIFICATION GUIDELINES IN THE PROTOCOL.
 |
| | Consistency with Trial Treatment Profile | Is the clinical/pathological presentation of the AE consistent with previous knowledge regarding investigational product(s) or drug class pharmacology or toxicology? |
| | | The assessment of relationship will be reported on the case report forms /worksheets by an investigator who is a qualified physician according to his/her best clinical judgment, including consideration of the above elements. |
| Record one of the following | | Use the following scale of criteria as guidance (not all criteria must be present to be indicative of investigational product(s) relationship). |
| Yes, there is a reasonable possibility of investigational product(s) relationship. | | There is evidence of exposure to investigational product (s). The temporal sequence of the AE onset relative to the administration of investigational product(s) is reasonable. The AE is more likely explained by investigational product(s) than by another cause. |
| No, there is not a reasonable possibility of investigational product(s) relationship | | Subject did not receive the investigational product OR temporal sequence of the AE onset relative to administration of investigational product(s) is not reasonable OR the AE is more likely explained by another cause than the BMS product. (Also entered for a subject with overdose without an associated AE.) |

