6.2 DOSING DELAYS/DOSE MODIFICATIONS

6.2.1 Metformin

The following guidelines are provided for the modification of the dose of metformin in the event of toxicities attributed by the investigator to this study drug. Toxicities unrelated to metformin will not ordinarily result in the modification of dose. AEs will be defined based on the National Cancer Institute (NCI) Common Terminology Criteria for Adverse Events (CTCAE) version 4.

In general, subjects experiencing **Grade 1 and 2** drug related toxicities should not have the dose of metformin modified. However, appropriate supportive care should be provided for the management of drug related toxicities. Grade 2 toxicities may require dose or schedule modifications (delaying or omitting individual doses) due to potentially greater clinical significance; however, this should occur after discussion with study PI.

Dosing of metformin must be delayed if a subject experiences a **Grade 3 non-hematologic** toxicity. If the toxicity resolves (returned to baseline or decreased to Grade ≤ 1) within 7 days, dosing of metformin may be resumed one lower dose level (See section 6 Table 3). Exceptions to this rule are as follows:

- Grade 3 fatigue: dose modification is left to the PI's discretion;

- Grade 3 nausea, vomiting and diarrhea: dose modification only after optimal prophylactic measures have failed to control the symptoms adequately;

In the case of Grade 4 **non-hematologic** toxicity, **or persistent Grade 3** toxicity despite one dose level reduction, metformin will be discontinued.

No dose adjustment of metformin will be performed for anemia.

No dose adjustment for Metformin will be performed for grade 1, 2, or 3 neutropenia or grade 1, 2, or 3(without bleeding) thrombocytopenia.

Dosing of metformin will be delayed if subjects develop grade 4 neutropenia or grade 3 thrombocytopenia complicated by bleeding or grade 4 thrombocytopenia. If the toxicity resolves (returned to baseline or decreased to Grade ≤ 1) within 14 days, dosing of metformin may be resumed one lower dose level (See section 6 Table 3).

Table 3: Dose reduction of Metformin

| Dose Level | Metformin |
|-------------------|------------------------|
| 1 | 1000 mg AM/1000 mg PM |
| -1 | 500 mg AM/1000mg mg PM |
| -2 | 500 mg AM/500mg mg PM |

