6.2.2 Nivolumab

Adverse events (both non-serious and serious) associated with nivolumab exposure may represent an immunologic etiology. These adverse events may occur shortly after the first dose or several months after the last dose of treatment. nivolumab must be withheld for drug-related toxicities and severe or life-threatening AEs as per 3 below. See Section 6.6.1 for supportive care guidelines, including use of corticosteroids.

Toxicities unrelated to nivolumab will not ordinarily result in the modification of nivolumab dose. AEs will be defined based on the National Cancer Institute (NCI) Common Terminology Criteria for Adverse Events (CTCAE) version 4.

[figure not shown]
Dose Modification Guidelines for Drug-Related Adverse Events- Nivolumab

1. Corticosteroid taper should be initiated upon AE improving to Grade 1 or less and continue to taper over at least 4 weeks.
2. For situations where Nivolumab has been withheld, Nivolumab can be resumed after AE has been reduced to Grade 1 or 0 and corticosteroid has been tapered. Nivolumab should be permanently discontinued if AE does not resolve within 12 weeks of last dose or corticosteroids cannot be reduced to ≤ 10 mg prednisone or equivalent per day within 12 weeks.
3. For severe and life-threatening irAEs, IV corticosteroid should be initiated first followed by oral steroid. Other immunosuppressive treatment should be initiated if irAEs cannot be controlled by corticosteroids.

4. Myocarditis: Withhold treatment for Grade 1 or 2. Permanently discontinue for Grade 3 or 4. Based on severity of AE administer corticosteroids.
5. Newly developed Type I diabetes mellitus: Follow endocrinopathy adverse event management algorithm. Permanently discontinue Nivolumab if associated hyperglycemia is grade 4.
6. Dosing interruptions are permitted in the case of medical / surgical events or logistical reasons not related to study therapy (e.g., elective surgery, unrelated medical events, patient vacation, and/or holidays). Subjects should be placed back on study therapy within 3 weeks of the scheduled interruption, unless otherwise discussed with the Sponsor-investigator. The reason for interruption should be documented in the patient's study record.

GI Adverse Event Management Algorithm

[figure not shown]

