9.1.2 Metformin ER

Metformin will be bought by the investigational pharmacy services at Winship Cancer Institute and the funding will be provided by BMS.

The investigator shall take responsibility for and shall take all steps to maintain appropriate records and ensure appropriate supply, storage, handling, distribution and usage of investigational product in accordance with the protocol and any applicable laws and regulations.

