10.2 Statistical and Analytical Plans

Summary statistics will be presented for all safety, efficacy and biomarker parameter analyses. The purpose of these analyses is hypothesis generating. Various exploratory statistical tests may be applied to data generated from this trial to generate hypotheses to be tested in subsequent trials. In general, data for continuous parameters will be presented using descriptive statistics including sample size, mean, and median; standard deviation; and minimum and maximum. Categorical parameters be displayed using counts and percentages. Toxicities will be presented as worst toxicity per patient and will be reported as percent toxicity.

Objective response rate will be calculated as proportion (Responders/Total patients) along with 95% confidence intervals using the Clopper-Pearson method. Chi-square test or Fisher's exact test will be used to compare the efficacy in term of response rate, biochemical response (CEA) between the different groups stratified by biomarkers or other factors, respectively. Logistics regression

model will be further employed to test the adjusted effect of biomarkers on the response rate after adjusting for other clinical factors and demographic factors.

For progression free survival, progression or death from any cause will be defined as the event. Patients will be censored at time of last follow-up. For overall survival, death from any cause will be defined as the event. Patients will be censored at time of last follow-up. Overall survival (OS) and progression free survival (PFS) rates of two patient groups stratified by response or other factors will be estimated with the Kaplan-Meier method and compared between different groups using the log-rank test, respectively. The PFS and OS of each patient group at specific time points, such as 6 months, 1 year, 3 year, and 5 year, etc. will be also estimated alone with 95% CI. Cox proportional hazards models will be further used in the multivariable analyses to assess adjusted effect of response on the patients' OS and PFS after adjusting for other factors. Interaction terms between these factors will also be tested for statistical significance. The proportional hazards assumption will be evaluated graphically and analytically with regression diagnostics. Violations of the proportional hazards assumptions will be addressed by use of time-dependent covariates or extended Cox regression models.

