10.4 Analysis Sets

All subjects who receive any amount of study drug will be included in the evaluation of safety and efficacy.

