10.6 Safety Analysis

10.6.1 Adverse Events

Adverse events will be classified using MedDRA System Organ Classes and Preferred Terms. Furthermore, SAEs, AEs with a severity grade of 3 or above using NCI CTCAE version 4.0, AEs deemed related to study drug, AEs leading to discontinuation of study drug, and AEs leading to death will also be summarized in preferred term by system organ class and listed on an individual subject basis.

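### Table 6 judges causality partly against investigational product(s) and partly against the BMS product, and no scale records relatedness by drug, so the related-AE table may undercount metformin events and cannot be split by agent

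*Combined protocol and SAP*

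**What the plan says.** Table 6 in section 8.3.2 instructs the investigator to "Record one of the following" and offers a Yes and a No verdict, both headed by a reasonable possibility of relationship to the investigational product(s). The causal statement in the Yes row is also framed against investigational product(s). The No row has three alternatives joined by OR. The first two refer to the investigational product(s). The third is met when "the AE is more likely explained by another cause than the BMS product". The term BMS product recurs in the lead-in to the causality components and in the dechallenge and rechallenge notes.

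The supply sections separate the drugs. Section 9.1.1 has BMS providing nivolumab. Section 9.1.2 says "Metformin will be bought by the investigational pharmacy services at Winship Cancer Institute", with BMS paying. Sections 6.1.2 and 6.5 treat both as investigational agents.

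A second binary scale in 8.2.1.1 defines Related and Not related against study drug and applies to all adverse events.

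The dose-modification rules work by drug. Section 6.2.1 applies "in the event of toxicities attributed by the investigator to this study drug", meaning metformin. Section 6.2.2 says "Toxicities unrelated to nivolumab will not ordinarily result in the modification of nivolumab dose". Section 6.6.1 applies its guidance to events judged related to nivolumab. Section 10.6.1 then summarises "AEs deemed related to study drug", with no split by agent.

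**The concern.** A causality scale should lead two careful physicians with the same facts to the same answer. Here the Yes row and one sufficient part of the No row measure against different things, so a metformin-caused event may be coded either way. The field also carries one answer for two drugs, while three sections of the protocol act on attribution to one drug or the other.

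The verdict feeds a planned analysis. If some metformin events are coded unrelated, the related-AE table in 10.6.1 is too low for that drug. Even if every event is coded Yes, the table cannot show which drug was held responsible, and the causality record cannot confirm that the dose-modification section applied was the one matching the attribution.

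**Working it through.** There is no figure to reproduce. The check sets the passages side by side and runs three cases through them, taking BMS product to mean nivolumab.

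**Case A: an event caused by metformin in the lead-in (Day -14 to Day -1).** Metformin is the only study drug taken.

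| Test | Comparator | Met? |
|---|---|---|
| Table 6, Yes row, causal statement | investigational product(s) | Yes; metformin is one |
| Table 6, No row, first alternative | no investigational product received | No |
| Table 6, No row, second alternative | unreasonable timing relative to investigational product(s) | No |
| Table 6, No row, third alternative | a cause other than the BMS product | Yes; the cause is metformin |
| 8.2.1.1 | study drug | Related |

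The No alternatives are joined by OR, so the third is enough by itself. Table 6 therefore supports both verdicts, while 8.2.1.1 supports only one.

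**Case B: combination treatment; metformin is stopped, nivolumab continues and the event resolves.** The main dechallenge question asks about investigational product(s), so this is a positive dechallenge. The note beneath it makes the criterion not applicable when the event improved despite continuation of the BMS product. Read literally, that sets aside evidence pointing to metformin. This case is about how Table 6 treats the evidence, not about how the event should be managed.

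**Case C: an event on combination treatment coded Yes.** The single answer is compatible with attribution to nivolumab, to metformin or to both. Sections 6.2.1 and 6.2.2 need to know which. The scale in 8.2.1.1 has the same limit, and no section calls for a relationship entry for each drug.

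**Dependence on the reading.** BMS product is never defined. If it is read to include metformin, because BMS funds the purchase, the conflicts in cases A and B disappear. Case C does not, because it rests only on there being one verdict for two drugs.

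**The case against.** The strongest reply is that no sensible investigator would code metformin toxicity as unrelated. The heading of the No row, the question that opens the relationship section of Table 6, and the Yes row all refer to investigational product(s). The criteria are described as guidance, to be used with clinical judgment. Section 8.2.1.1 has a clean definition against study drug, the same term as in 10.6.1. BMS product looks like leftover template wording. This stands as far as it goes: miscoding is permitted, not required, and the route from the No row to the 10.6.1 table is possible rather than certain.

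It is also fair that the case report form is not in the documents and might already hold two fields; that investigators must attribute by drug in practice to apply 6.2.1 and 6.2.2; and that 10.6.3 summarises the main reasons for dose modifications. None of this makes the plan require a causality entry per drug or a related-AE table by drug.

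Adverse events are collected whether or not judged related, and 10.6.1 tabulates serious events, events of grade 3 or above, discontinuations and deaths regardless of relatedness. Metformin toxicity is not lost from the safety report.

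A reader might infer three stronger things that the documents do not support:

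- **A patient count.** The 12.9% for diarrhoea and 8.2% for nausea/vomiting in 4.2.2 are listed adverse-event incidences from a 16-week placebo-controlled study in type II diabetes. The same list includes influenza and upper respiratory infection, and no placebo rate is given. Multiplying them by 28 would not estimate metformin-caused events.
- **An overlap on colitis.** Colitis is listed for nivolumab in 4.2.1 but not for metformin in 4.2.2.
- **A lost answer on whether adding metformin changes tolerability.** The trial is single-arm, has no nivolumab-alone control and states no such objective. Better coding would not supply that comparison.

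**Conclusion.** The point holds as a defect of wording and recording that reaches one planned safety table. Table 6 is internally inconsistent for a two-drug regimen and can conflict with 8.2.1.1. Neither scale captures attribution by drug, although the dose-modification and supportive-care sections rely on it. The related-AE summary in 10.6.1 may therefore undercount metformin-related events and, as specified, cannot be split by agent.

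The possible undercount rests on reading BMS product as nivolumab, an inference from 9.1.1 and 9.1.2. The missing split does not depend on that reading. No number of affected events can be derived from the documents. The effect is confined to the related subset of adverse events; the primary endpoint and the relatedness-free safety tables are untouched. The change should be made, but it is a modest one.

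**What to change.** 1. In Table 6, replace BMS product with investigational product(s) (nivolumab and/or metformin) throughout: the lead-in to the components, the dechallenge and rechallenge notes, and the No row.
2. Align Table 6 with the definitions in 8.2.1.1, so that one scale applies to every adverse event.
3. Record the relationship separately for nivolumab and for metformin for each event.
4. In 10.6.1, tabulate related adverse events by drug.

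An optional display would show events before and after the first nivolumab infusion. Section 10.2 says "Toxicities will be presented as worst toxicity per patient and will be reported as percent toxicity" and plans no split by period, and 10.4 says "All subjects who receive any amount of study drug will be included in the evaluation of safety and efficacy", so a patient who leaves during the lead-in counts in the safety set. Table 6 already records start and stop dates, so this needs no new data.

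The cost is one extra field on the adverse-event form, some wording, a few table columns and slightly more investigator work per event. No dose or clinical rule changes.
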